1.6 Health-related Quality of Life (HRQOL) and Economic Analysis

In the United States, total national health expenditures (NHE) increased from \$7.14 billion in 1990 to \$2.23 trillion in 2007, which represents an average annual growth rate of 7.0%. In contrast, over the same period, U.S. gross domestic product (GDP) increased from \$5.8 trillion in 1990 to \$13.8 trillion, or average 5.2% annual growth rate. Given that national health expenditures have grown faster than GDP, the share of GDP devoted to health expenditures has increased from 12.3% in 1990 to 16.2% in 2007 [74]. Moreover, national health expenditure growth is expected to continue to outpace income growth, with total NHE reaching \$4.35 trillion by 2018, accounting for 20.3% of GDP (CMS 2009). There is growing concern that these trends in health expenditures are not sustainable. For the Medicare program, current estimates of the present value of total unfunded liabilities through the year 2083 (the present value of the difference between projected future Medicare expenditures and Medicare revenues over the next 75 years under current Medicare policy) total \$89 trillion, with Medicare's Hospital Insurance ("Part A") trust fund projected to be depleted by 2017 [75].

Prior studies have estimated that about half of the recent growth in health expenditures is attributable to advances in various forms of health technology, including new pharmaceutical products, surgical procedures, imaging modalities, and new biomarkers [75]. While almost all of these new technologies offer some potential to improve clinical outcomes, they also more often than not add to health expenditures. Within the context of unsustainable trends in health expenditures, a key policy question relates to whether the extent of improvement in outcomes associated with the use of a new technology is attained at a "reasonable" additional cost,

compared to existing technology. Indeed, the value offered by new technologies is being subjected to increasing scrutiny by reimbursement authorities in many health systems worldwide. For example, in the United Kingdom, the National Health Service bases payment policy decisions for new technologies on recommendations from the National Institute for Health and Clinical Excellence (NICE), which in turn are substantially influenced by cost-effectiveness analysis yielding an estimated additional “cost per quality-adjusted life-year (QALY) gained” via use of the new technology. Currently, NICE usually considers technologies offering improved outcomes at a cost less than £20,000 to £30,000 per QALY gained (about \$33,000 - \$50,000) acceptable, though exceptions are common[76].

Several recent studies have evaluated health-related quality of life (HRQoL) for biologics and targeted treatment for mRCC. In the Sunitinib versus INF-alpha trial, health-related quality of life was superior in the Sunitinib group as assessed by the FKSI-15, FACT-G, and EQ-5D [3][80]. In a review article regarding quality-of-life in patients with recent renal cell by Cella et al., it is clear that quality-of-life measures are increasingly being utilized within the clinical trial setting to assess quality adjusted life year expectancy [81]. Two recent trials evaluating health-related quality of life for Sorafenib utilizing the FACT-FKSI, FACT-G, and EQ-5D indicated that Sorafenib resulted in improvements in individual items related to registry function and quality of life compared with placebo [82]. Additionally, European trials evaluating temsirolimus in a phase 3 setting versus INF-alpha or both, showed quality adjusted survival favoring patients who received temsirolimus [83]. In a group of heavily pretreated metastatic renal cell cancer patients enrolled on a phase 3 trial comparing everolimus versus placebo, quality of life as measured by EORTC QLQ C30 and FKSI-DRS showed no changes between the two treatment groups showing stable quality-of-life as compared to placebo [84]. Additionally, there are ongoing studies evaluating QoL in patients receiving axitinib as well.

Due to the high cost of these new therapeutic agents several cost-effectiveness studies have evaluated the cost per quality adjusted life year of first-line therapeutic options of metastatic renal cell carcinoma. In an economic analysis of sunitinib versus INF-alpha and IL-2, Sunitinib was shown to be a cost-effective alternative to INF-alpha and IL-2 from a US societal perspective [85]. An economic analysis from the Chinese perspective was undertaken evaluating INF-alpha, IL-2, INF-alpha plus IL-2, sunitinib, and bevacizumab plus INF-alpha, and it showed that sunitinib was cost effective when the willingness to pay threshold was over \$16,000 which would be appropriate for several developed regions within China [86]. Given the rising costs associated with the biologic and targeted therapies for metastatic renal cell carcinoma, the cost implications of this protocol warrant further study.

Therefore, we propose to evaluate patients' health related quality of life (HR-QoL) and health resources utilization in order to evaluate the economical consequence of using the treatment proposed in this study and its impact on quality adjusted survival. Based on the primary hypothesis of this study that response rates will be improved with the combination of SABR and Nivolumab, we further hypothesize that the addition of SABR will increase the durability of response or lengthen the time to progression, thus increasing the cost effectiveness of the combined therapies. Thus, we hypothesize that upfront SABR, while adding modestly to the total cost of the combined therapies, may be cost saving over the patient's entire treatment course compared to Nivolumab alone, making the combination a very attractive treatment for mRCC patients. Additionally, we hypothesize that combination therapy will increase the quality-adjusted life-years for mRCC cancer patients (compared to the prior reported chemotherapeutic, biologic, and targeted options for mRCC) at a reasonable incremental cost, as defined by generally accepted cost-effectiveness thresholds. The sample size would be prohibitively large should these secondary endpoints be analyzed beyond simple descriptive statistical purposes.

2.0 STUDY OBJECTIVES

This study is a safety lead-in phase II single institution clinical trial using Nivolumab and concurrent SABR to 1-6 metastatic sites in patients with metastatic clear cell renal cell cancer (mccRCC) who have received at least one prior anti-angiogenic therapy. Nivolumab will be dosed intravenously as per the institution guidelines, until disease progression, unacceptable toxicity or other reasons specified in the protocol. No dose modifications for Nivolumab will be allowed. SABR will be administered to 1-6 sites of metastatic disease one week after the first dose of

Nivolumab with a single (24-27 Gy) or three (11-16 Gy/fraction) fractions. The sites of larger (bulky) disease and the sites of symptomatic disease will be prioritized for treatment at the discretion of the treating radiation oncologist.

2.1 Primary Objectives

The primary objective of the interim safety analysis of the trial (6 patients) is feasibility, safety and toxicity. The primary objective of the phase II portion of the trial will be to increase the historical RR of treatment with Nivolumab alone by 75% with the addition of SABR. The assessment of RR will be based on the evaluation of RECIST criteria and radiated lesions will be excluded from target lesions. The reported RR for Nivolumab for RCC is 25% [5, 31]; an increase of 100% will lead to a RR of about 50%. Therefore, the hypothesis of the phase II trial is that **concurrent administration of SABR will increase the RR of Nivolumab to 50% for mRCC in patients who have failed one prior anti-angiogenic therapy.**

Treatment with immunotherapies has been reported to cause a “tumor flare” which denotes the apparent radiographic increase in tumor burden or occurrence of new lesions before a true clinical response can be established. This “flare” is thought to be due to a transient increase in immune cell infiltration while the immune system is being primed. Therefore, RECIST criteria may fail to accurately report RR and some patients will be taken off therapy before a true response is measured. In the CheckMate 025 trial, 44% of patients who progressed per RECIST criteria were continued on Nivolumab if they were thought to have clinical benefit. In addition, in the phase II trial of Nivolumab dose escalation trial, treatment beyond first RECIST-criteria progression was allowed in patients who tolerated Nivolumab and exhibited investigator-assessed clinical benefit. 17%, 22% and 26% of patients in the 0.3, 2 and 10 mg/kg groups were treated beyond progression. Median number of doses received after RECIST progression was 4.5, 7.5 and 8.5 in the 0.3, 2 and 10 mg/kg groups. Median PFS was 2.7 mos, 4.0 mos and 4.2 mos in the 0.3, 2 and 10 mg/kg groups using the RECIST criteria but increased to 4.3, 5.4 and 6.9 mos respectively using immune-response PFS. In a subgroup analysis, 69% (25/36) of patients who received treatment beyond first progression, defined as patients receiving their last Nivolumab dose >6 weeks after RECIST-defined progression, demonstrated sustained reductions in tumor burden or lesion stabilization with an acceptable safety profile. Median OS for patients treated beyond first progression was 22 mos vs 12 mos for those not treated. Thus, patients will be allowed to stay on Nivolumab after their first RECIST-criteria progression per the treating physician. Data will be evaluated using the RECIST criteria for primary endpoint and ir-RECIST for secondary endpoint.

2.2 Secondary Objectives

- 2.2.1 RR based on ir-RECIST
- 2.2.2 To evaluate overall survival (OS), which is defined as the time between date of registration and the date of death due to any cause. In analyzing OS, we will take into account the MSKCC prognostic criteria for mRCC and compare our data to historical controls in the appropriate risk category
- 2.2.3 To evaluate progression free survival (PFS), which is defined as the time between date of registration and the first date of documented disease progression or date of death due to any cause
- 2.2.4 To evaluate complete response rate, which is defined as the percentage of patients who show complete response as per ir-RECIST criteria
- 2.2.5 To evaluate time to progression (TTP), which is defined as time between date of registration and date of documented progression.
- 2.2.6 To evaluate median response duration, which is defined as the time between the date a response (CR or PR) was first seen until date of progression
- 2.2.7 To evaluate the tolerability and toxicity as measured according to CTCAE v4.0.
- 2.2.8 To measure the improvement in health-related quality of life (HR-QoL)

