2.4 Endpoints

- 2.4.1 **Response:** Treatment response will be measured using both the RECIST and immune related RECIST criteria (ir-RECIST), a minor modification of RECIST 1.1 for immunotherapy [89]. Radiated lesions will be excluded from target lesions.
- 2.4.2 **Death:** Death due to any cause, although in mRCC patient population, the overwhelming majority is expected to be secondary to disease progression.
- 2.4.3 **Progression:** Progression will be defined according to the ir-RECIST criteria and verified by a second set of imaging at least 6 weeks apart.
- 2.4.4 **Immune Response:** Immune response will be measured using ELISpot assay, T-cell proliferation assay and ELISA.
- 2.4.5 **Toxicity:** Toxicity will be measured using CTAE v4.0

- 2.4.6 HR-QoL:** HR-QoL will be measured using FACT-G, EQ-5D and FKSI questionnaires at baseline, and at different time-points during treatment and follow up
- 2.4.7 Cost-effectiveness analysis:** Health care utilization data needed to assess costs will be obtained from patients' insurance claims during and after treatment. Markov modeling with probabilistic sensitivity analysis will be used to correlate quality-adjusted survival and cost.

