4.4 Duration of Follow Up

For patients who respond to treatment, subjects will be followed for five years or until death (although findings will be analyzed and reported at a median follow up of 2-4 years), whichever occurs first. For these patients, follow-up will be every 8 - 12 weeks from study registration with imaging studies and physical exam (recommended) every 8-12 weeks for the first year, then every 8-12 weeks for the second year, then every four-six months thereafter for a total of five years.

Subjects who show progressive disease will be followed for survival and will no longer strictly adhere to study calendar requirements.

Subjects removed from treatment for unacceptable adverse events will be followed until resolution or stabilization of the adverse event.

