5.3 Follow-up Procedures

- For patients who are still receiving Nivolumab:

Subject will be followed every 8-12 weeks starting from the date of registration for the first two years. , then every four-six months thereafter for five years or death, whichever comes first. The following procedures will be performed at each follow up:

- Physical exam (recommended), Performance Status (recommended), Vital Signs, Medication Review, AE assessment
- HR-QoL questionnaire at baseline, and then at six month intervals until patient meets primary endpoint
- Blood collection for correlative immunologic studies (see section 9.0): In total, all patients will get blood draws for correlative studies at baseline, follow up q 8-12 weeks (until discontinued or within first year of enrollment, whichever is first) and at 1 year (if discontinued before 1 year).
- Radiographic imaging: Tumor assessments will be completed by the investigator using the RECIST and ir-RECIST criteria as above.
 - CT chest, abdomen and pelvis with IV contrast (contrast recommended), if allowable by renal function. MRI with contrast (contrast recommended) can replace CT.
 - MRI, if necessary to confirm CT findings, at the discretion of physician

- For patients who have been discontinued from Nivolumab (See Section 4.3): Subject will be followed within 3 months from last dose ((+/- 2 months), or may be on date of discontinuation).

The following procedures will be performed:

- Physical exam (recommended), Performance Status (recommended), Vital Signs, Medication Review, AE sssessment
- Subsequent anti-cancer treatment/s
- Blood samples for correlation immunologic studies

After that, survival visits/phone calls continue annually to include Survival Status, AE Assessment, and Subsequent anti-cancer treatment/s.

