6.1.6 Duration of Response

Duration of overall response: The duration of overall response is measured from the time measurement criteria are met for CR or PR (whichever is first recorded) until the first date that recurrent or progressive disease is objectively documented (taking as reference for progressive disease the smallest measurements recorded since the treatment started).

The duration of overall CR is measured from the time measurement criteria are first met for CR until the first date that recurrent disease is objectively documented.

Duration of stable disease: Stable disease is measured from the start of the study registration until the criteria for progression are met, taking as reference the smallest measurements recorded since the treatment started.

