11.3 Data Analyses Plans

Exact binomial method will be used to calculate the response rate, toxicity rate, CR rate, and the corresponding 95% confidence interval. [Exact binomial test will be used to investigate if the response rate of the treatment arm is significantly different from that of historical control.](#) PFS and OS will be estimated using the Kaplan-Meier approach along with the 95% confidence interval using Greenwood's formula. One sample log-rank tests will be conducted to investigate if OS or PFS in the treatment arm is significantly different from that of historical control.

Generalized estimating equation (GEE) analysis will be conducted to investigate if there are significant changes in surrogate makers such as CD25, CD71, CD45RO, CD107a, CD54, CD69, Ki67, ICOS/CD278 and PBMC over time. HRQoL, CEA and quality adjusted survival time analysis is described in Section 10.

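### Duration of response leaves out death and has no censoring rule; if responders' deaths without documented progression are censored, the median will exceed the median time to progression or death

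*Combined protocol and SAP*

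**What the plan says.** Two places define duration of response. Objective 2.2.6 gives it as "the time between the date a response (CR or PR) was first seen until date of progression". Section 6.1.6 measures it from when the criteria for CR or PR are met "until the first date that recurrent or progressive disease is objectively documented", and its separate sentence on duration of CR is built the same way. Neither mentions death.

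PFS is defined differently. Objective 2.2.3 runs to "the first date of documented disease progression or date of death due to any cause", and section 6.1.7 agrees. Time to progression (TTP, 2.2.5) is, like response duration, progression-only.

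On analysis, section 11.3 states that "PFS and OS will be estimated using the Kaplan-Meier approach". It names no estimator and no censoring rule for response duration. Section 11.1 does not include response duration in its list of secondary endpoints.

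On deaths, section 2.4.2 counts all causes and says that "the overwhelming majority is expected to be secondary to disease progression". The documents give no rate for death without documented progression.

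**The concern.** A responder who dies before progression is documented has a PFS event on the date of death but, as the definition stands, never reaches the end of response. The analyst must then choose what to do with that patient, and the plan does not say. The usual result of applying Kaplan-Meier to a progression-only event is censoring at death, which treats the response as if it could have continued. Since section 2.4.2 expects most deaths to come from the disease, many readers would regard such a death as a failure of response.

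Durability is part of the trial's argument. Section 1.4.2 hypothesises a durable effect of the combination, and section 1.6 links longer response to cost-effectiveness. A median that leaves these deaths out would look more favourable than the time that patients spend alive and in response.

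**Working it through.** **1. The plan's own figure.** None is stated for response duration. The only design figure is in section 11.2: 19 patients, 80% power, response rate 25% against 50%, two-sided level 0.2. With 0.1 in the upper tail, the exact rule at n = 19 is 8 or more responses, with upper-tail probability 0.0775 under 25% and power 0.820 under 50%. The sample size reproduces. It matters here only because it sets the number of responders: 19 × 0.50 = 9.5, or 19 × 0.25 = 4.75 if there is no improvement.

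**2. Can a responder die without documented progression?**
- Section 2.4.3 requires progression to be "verified by a second set of imaging at least 6 weeks apart", so a patient can die between the two scans.
- Section 6.1.4.3 provides for symptomatic deterioration without objective progression.
- Section 5.3, for patients off nivolumab, lists one visit without imaging, after which "survival visits/phone calls continue annually to include Survival Status".
- Against this, section 4.4 says of responders that "subjects will be followed for five years or until death", with imaging every 8 to 12 weeks for two years and every four to six months after that.

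Such deaths are therefore possible, but how often they would occur cannot be derived from the documents.

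**3. Size if such deaths are censored.** Assume constant cause-specific hazards in responders: λp for documented progression and λd for death without it. Let f = λd/(λp + λd).
- Median with deaths censored: ln 2/λp.
- Median time to progression or death: ln 2/(λp + λd).
- Ratio: (λp + λd)/λp = 1/(1-f).

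| Assumed f | 1/(1-f) | A 12-month median to progression or death (illustrative) is reported as |
|---|---|---|
| 0% | 1.00 | 12.0 months |
| 5% | 1/0.95 = 1.05 | 12.6 months |
| 10% | 1/0.90 = 1.11 | 13.3 months |
| 20% | 1/0.80 = 1.25 | 15.0 months |
| 30% | 1/0.70 = 1.43 | 17.1 months |

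**4. Other treatments that the silence leaves open.**
- *Death as a competing event.* The cumulative incidence of progression is (1-f)(1-exp(-λt)), with λ = λp + λd. Setting it to 0.5 gives t = -ln(1 - 0.5/(1-f))/λ. Divided by ln 2/λ, this is 1.17, 1.42 and 1.81 for f = 10%, 20% and 30%.
- *Excluding these patients.* Under constant hazards with complete follow-up, the time of the first event does not depend on its type, so the median is unchanged. However, responders are then dropped because of their outcome.

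**5. Sensitivity with few responders.** With 9 to 10 responders, f of 10% to 20% is one or two patients. A simulation (exponential times, 12-month median, 36-month cut-off, 8,000 trials per setting, median taken where the Kaplan-Meier curve first reaches 50% or less) compared censoring these deaths with counting them. The estimated median differed in this share of trials:

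| Assumed f | 10 responders | 5 responders |
|---|---|---|
| 5% | 23% | 9% |
| 10% | 41% | 18% |
| 20% | 68% | 36% |
| 30% | 84% | 51% |

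**The case against.** The strongest reply is that nothing in the plan says these patients are censored. A reader might infer that they are, and that the median is therefore overstated. The documents do not support that as fact: section 11.3 gives no rule, and exclusion would not lengthen the median under the assumptions above. This stands, so the conclusion must be conditional.

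The factor also needs careful reading. With independent constant hazards, censoring at death estimates time to progression correctly. The factor 1/(1-f) is thus the gap between two quantities, time to progression and time to progression or death. It does not measure bias from informative censoring, which nothing in the documents allows one to quantify. This stands too.

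A reader might also infer that the small number of responders makes the upward shift worse. It does not: 1/(1-f) contains no sample size. Small numbers make the estimate sensitive to single patients.

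The documents also limit f. Besides the imaging schedule in 4.4, section 6.1.4.3 asks for efforts to document progression after treatment stops. Pathologic fracture (unless at a treated site) and cord or cauda equina compression count as progression under 6.1.4.5 and 6.1.4.6. Section 4.2.1.1 dates confirmed progression to the first scan, so confirmation does not delay the date. If most deaths follow progression, as 2.4.2 expects, progression may often be documented first. These points make f smaller but do not make it zero, given 5.3.

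Finally, the difference from PFS is not in itself an error, since response duration matches TTP. But TTP already supplies the progression-only measure, and the definition of response duration still gives such a death no place.

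**Conclusion.** The point holds in conditional form. Sections 2.2.6 and 6.1.6 do not let death end a response, and section 11.3 does not say how response duration is estimated or censored. If deaths without documented progression are censored, the reported median exceeds the median time to progression or death by 1/(1-f), that is, by 5% to 43% for f between 5% and 30%. This rests on constant hazards and on an assumed f, and there is no effect if f = 0. With about 9 to 10 responders at a 50% response rate, one or two such deaths can shift the estimate. Response duration is a secondary endpoint with no test or target, and PFS and OS, which both count death, are also to be reported. The consequence is limited to how durability is described.

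**What to change.** In 2.2.6 and 6.1.6, define duration of response as the time from first CR or PR to first documented progression or death from any cause, whichever is first. In 11.3, specify Kaplan-Meier among responders, with those alive and progression-free censored at their last tumor assessment. TTP may stay as the progression-only measure.

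The cost is a wording change. Death dates are already needed for OS, so no new data are collected. The downside is that the reported median may be shorter. Label: cheap improvement.
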